11.1 Sample Size Determination

We do not specify *a priori* sample size since we will be assessing recruitment, study procedures and retention in order to inform the planning of a larger trial at a future date. We will pause recruitment when we have a minimum of 10 participants in each arm (about 40 participants in total).

At that point we will perform an interim analysis of both the quantitative and qualitative data obtained and determine whether we have enough outcome measures to meet the primary objective. This decision will be taken by the study steering group which will comprise all of the investigators and the study co-ordinator. The decision will be based on whether the data obtained is sufficient to fully inform the design of the larger trial to follow, specifically whether the methodology is acceptable to participants and study staff and whether the intervention adherence measures are capturing data as intended. We have expertise in qualitative methodology in the study steering group.

If the group feel that we have sufficient data to achieve the primary objective, the study will be stopped and the exploratory outcome data will be analysed. If the group feel further data is needed, we will not analyse exploratory outcome data at this point and recruitment will resume until a minimum of 20 patients per arm have been recruited (about 80 participants in total). When data collection is complete, we will perform a final analysis of all primary and exploratory outcome data.

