9.4 Subsequent visits

**University of
Nottingham**
Health Service

At day 28 and 168 after visit 1, participants will be asked to provide a further 15ml blood sample to measure immunological and biochemical responses.

Participants in the optional immunology subgroup cohort may be invited to have a larger blood sample (up to 60ml) collected at day 28.

A qualitative nested interview study will be used to assess participants', clinicians' and other stakeholders' views on intervention and trial acceptability and determine the barriers and facilitators to implementing the intervention in routine care. The process for obtaining participant informed consent for the study will include consent for potential inclusion in the qualitative interview nested study. The qualitative study will be reported in line with the Consolidated Criteria for Reporting Qualitative Research (COREQ: Tong et al, 2007).

We will conduct semi-structured interviews with a sample of patient participants and stakeholders (healthcare professionals, or other practice staff involved in explaining the trial to patients, conducting the screening and consent processes, or delivering the intervention). We aim to complete these within 4 weeks of the end of the intervention period. Interviews will be conducted by telephone, video call or face-to-face at participant preference, audio-recorded (with permission) and transcribed verbatim. Topic guides will be developed based on study aims and input from the Trial Management Group (TMG). Interview participants will be selected purposively to ensure diversity in relevant characteristics (e.g., trial group allocation, age, gender, ethnicity, deprivation index, region). Sampling will cease when we have sufficient information power relevant to the study aims (Malterud et al, 2016) although we anticipate up to 20 participants, and 10 stakeholders. Analysis of qualitative data will use appropriate methods such as inductive thematic analysis.

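### The interim stop rule in Protocol 11.1, read literally, ends follow-up and starts the exploratory analysis before the 24-week data are complete, and has no branch for a methodology found unacceptable

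*Protocol*

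**What the plan says.** Protocol section 11.1 sets the trigger for the interim by numbers enrolled: "We will pause recruitment when we have a minimum of 10 participants in each arm (about 40 participants in total". It continues: "At that point we will perform an interim analysis of both the quantitative and qualitative data obtained". No minimum follow-up is attached to that step.

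The decision has two branches.

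- **Stop.** "If the group feel that we have sufficient data to achieve the primary objective, the study will be stopped", and the exploratory outcomes are then analysed.
- **Continue.** If the group wants more data, the exploratory outcomes are left unanalysed at the interim and "recruitment will resume until a minimum of 20 patients per arm have been recruited (about 80 participants in total". A final analysis of all outcomes follows once data collection has finished.

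The test is whether the data are enough to design the larger trial. It is spelled out as "specifically whether the methodology is acceptable to participants and study staff" and whether the adherence measures are working as data-capture tools. On who decides: "This decision will be taken by the study steering group which will comprise all of the investigators and the study co-ordinator".

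Other sections fix the follow-up. The Synopsis lists the primary outcome at 4 weeks and the exploratory antibody outcome at 4 and 24 weeks. Section 7 gives durability of protection as a reason for the 6-month sample. Section 9.4 states: "At day 28 and 168 after visit 1, participants will be asked to provide a further 15ml blood sample". Section 10 runs safety reporting to day 168. Section 9.9 ends the study with the analysis of the final blood sample.

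**The concern.** The stop branch ends the study and moves straight to the exploratory analysis. If it is followed as written, participants who have not reached day 168 lose their last sample and the rest of their safety follow-up, and the exploratory analysis runs on incomplete 24-week data. At stake are the durability outcome and the assessment of retention, which section 11.1 itself names as a purpose of the trial.

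The second concern is the form of the test. Having enough information and having a favourable answer are different things, yet the criterion for sufficiency is worded as acceptability. If the answer is that the methodology is not acceptable, the criterion as worded is not met, and the only other branch written down is to recruit to about 80. No branch says what to do when the design is found unacceptable.

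**Working it through.** **1. The plan's own figures.** There are four arms at 1:1:1:1 (section 7). 4 × 10 = 40 at the pause and 4 × 20 = 80 after extension, so both figures in 11.1 reproduce. The extension is 80 − 40 = 40 people.

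**2. Time points.** The primary outcome is at 4 weeks = 28 days, and the last sample is at 24 weeks = 168 days (Synopsis, 9.4). Interviews are planned within 4 weeks of the end of the intervention (9.4). For the 28-day vitamin D arms that means up to about day 28 + 28 = 56.

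**3. Follow-up outstanding at the interim.** Let the interim fall *d* days after the last of the 40 enrols. The protocol does not give *d*. The value 0 is the literal reading; 28 and 56 are assumptions matched to the primary outcome and the latest interviews.

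- Days left for the last participant: 168 − *d*.
- The first participant has been enrolled for the recruitment period plus *d* days, so nobody has a day-168 sample if recruitment took less than (168 − *d*)/7 weeks.

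| Interim at last participant's | Days left for that participant | Nobody has a day-168 sample if recruitment took under |
|---|---|---|
| day 0 | 168 | 24 weeks |
| day 28 | 140 | 20 weeks |
| day 56 | 112 | 16 weeks |

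**4. Share of the 40 who have reached day 168.** The recruitment period *W* (weeks) is not stated, and uniform accrual is assumed. The share is max(0, [*W* − (168 − *d*)/7] / *W*).

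| *W* | day 0 | day 28 | day 56 |
|---|---|---|---|
| 12 | 0% | 0% | 0% |
| 24 | 0% | 4/24 = 17% | 8/24 = 33% |
| 36 | 12/36 = 33% | 16/36 = 44% | 20/36 = 56% |
| 52 | 28/52 = 54% | 32/52 = 62% | 36/52 = 69% |

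At every recruitment length shown, the 24-week data are incomplete at the interim.

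**5. The two branches side by side.** Section 11.1 speaks of recruitment when it pauses and resumes, but of the study when it stops. The continue branch expressly holds back the exploratory analysis at the interim, which implies that the stop branch carries it out then. Only the continue branch waits for complete data collection.

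**6. The acceptability criterion.** A clear finding of unacceptability can be taken in two ways:

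- as a failed criterion, which leads to the continue branch and about 40 more people;
- as an answer that is enough to design the next trial, which leads to the stop branch.

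The text does not choose between them.

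**The case against.** The best defence is that only recruitment is meant to stop. Section 11.1 concerns sample size, and its language of pausing and resuming is about recruitment. Section 9.9 keeps the study open until the final sample is analysed, section 9.4 schedules the day-168 sample without exception, and nothing in 11.1 cancels a visit. This stands as a plausible reading, so a reader who infers that the protocol definitely abandons follow-up goes further than the documents allow. It does not remove the conflict: the stop branch names the study, and even on this reading it leaves the exploratory analysis without the wait for complete data that the other branch has.

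On acceptability, the governing test is whether the data suffice to design the larger trial, and a clear negative answer could meet it. Section 15.3 also provides for amendments. A reader might infer that the rule forces 40 more people into an unchanged design; the text permits that outcome but does not require it.

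A reader might also infer that feasibility can be declared at any level of adherence, so that numeric cut-offs and a member from outside the team are needed. Section 11.1 does not support this. It decides whether to collect more data, not whether the interventions are feasible, and it names two criteria. Its adherence criterion concerns how well the measures capture data, not the level of adherence. Numeric thresholds and outside membership are preferences in a feasibility study of about 40 people with a partly qualitative primary outcome.

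**Conclusion.** There is a real conflict between the stop branch of 11.1 and the follow-up set in the Synopsis, 9.4, 9.9 and section 10. Taken literally, the stop branch ends follow-up and triggers the exploratory analysis before the 24-week data are complete. With the interim assumed at the last participant's day 28 to 56, that participant has 140 to 112 days outstanding, and no day-168 sample exists for anyone if recruitment took under 20 or 16 weeks respectively. Incompleteness for the latest participants does not depend on recruitment speed; how many of the earlier ones are affected does.

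The secondary point holds in a limited form: the wording allows recruitment of about 40 more people after a clear finding that the methodology is unacceptable, because no branch covers that finding. The figures of 40 and 80 are unaffected. The rule is fixed in the protocol itself, so this is not detail left to an analysis plan.

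**What to change.** Three changes to section 11.1:

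- **Stop branch.** Replace the phrase with: *recruitment will close; all enrolled participants are followed to day 168, and the exploratory outcomes are analysed after the last day-168 sample.* Participants who withdraw remain covered by 9.8.
- **Timing of the interim.** State that it takes place once the 4-week primary data of the first 40 participants are in.
- **Unacceptable methodology.** Add that a clear finding that the methodology is not acceptable counts as sufficient data and closes recruitment.

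This needs protocol wording only. No sample size, visit or assay changes, since the day-168 sample is already planned. The downside is a later exploratory analysis in the stop branch: at least 140 days after an interim at the last participant's day 28, or 112 days after one at day 56. Dating the interim also makes explicit that the recruitment pause lasts at least 28 days after the last of the 40 enrols.

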11.2 Procedure for Accounting for Missing, Unused, and Spurious Data

Reasons for missing data (including withdrawal of consent or inability to obtain any laboratory results) will be indicated, but missing data will not be imputed.

11.3 Inclusion in analysis

Analysis will be conducted of a full data set for all participants who are deemed to have no major protocol violations that could interfere with the objectives of the study. Such a set will comprise all participants, who complete the e-diary (and consent form) and for whom post-baseline assessment of the primary outcome measure is available.

Laboratory data, such as blood samples, from all participants who enrol in the study will be included in the analysis.

**University of
Nottingham**
Health Service

12. Data management

The Chief Investigator will be responsible for all data that accrues from the study. All protocol-required information will be collected and into the CRF. CRF entries will be therefore considered source data. All other information will be entered onto their medical record and/or ISF. Source documents are original documents, data, and records from which the participant CRF data are obtained. For this study, these will include, but are not limited to, volunteer consent form, laboratory records, medical records, and correspondence. As part of the informed consent process, permission will be sought to access the participant's data from pertaining to basic demographic information and contact details.

All source data and participant files will be stored securely.

Direct access will be granted to authorised representatives from the Sponsor, host institution and the regulatory authorities to permit trial-related monitoring, audits and inspections. The study protocol, documentation, data, and all other information generated will be held in strict confidence. No information concerning the study, or the data will be released to any unauthorised third party, without prior written approval of the sponsor

Each study participant will retain the unique participant number first assigned at randomisation. Samples sent to laboratories for processing will be identified by participant number. All documents will be stored safely and securely in confidential conditions. Direct access will be granted to authorised representatives from the Sponsor and the UNHS and the regulatory authorities to permit study-related monitoring, audits and inspections. Participant name and any other identifying detail will NOT be included in any trial data electronic file.

The Investigators will maintain appropriate medical and research records for this trial, in compliance with GCP and regulatory and institutional requirements for the protection of confidentiality of volunteers. The Chief Investigator, co-Investigators and clinical research nurses will have access to records. The Investigators will permit authorised representatives of the Sponsor(s) and Host institution, as well as ethical and regulatory agencies to examine (and when required by applicable law, to copy) clinical records for the purposes of quality assurance reviews, audits and evaluation of the study safety and progress. Identifiable information such as contact details will be stored for a minimum of 5 years from the end of the study. Participants shall be approached should there be any unexpected safety signals emerging post-licensing surveillance. This includes storage of consent forms. Storage of these data will be reviewed every 5 years and files will be confidentially destroyed if storage is no

**University of
Nottingham**
Health Service

longer required. Considerations at the time of this review will include the value of retaining this information for participant safety, as a resource for the participants (e.g., if they wish to check which vaccines they have received in the study) and any regulatory requirements. De-identified research data may be stored indefinitely. If volunteers consent to be contacted for future research, a record of this consent will be recorded, retained and stored securely and separately from the research data. If volunteers consent to have their samples stored and used in future research, information about their consent form will be retained and stored securely as per Biobanking procedures and SOP.

Data collection tools will undergo appropriate validation to ensure that data are collected accurately and completely. Datasets provided for analysis will be subject to quality control processes to ensure analysed data is a true reflection of the source data. Trial data will be managed in compliance with local data management SOPs.

13. Quality assurance procedures

The study will be conducted in accordance with the current approved protocol, GCP, relevant regulations and standard operating procedures. Approved and relevant Standard Operating Procedures (SOPs) and Laboratory plans will be used at the laboratory site.

14. Protocol deviations and Serious breaches

Any deviations will be documented in a protocol deviation form and filed in the ISF. Each deviation will be assessed as to its impact on participant safety and study conduct. Significant protocol deviations will be listed in the end of study report.

A serious breach is defined as “A breach of GCP or the trial protocol which is likely to affect to a significant degree –

- (a) the safety or physical or mental integrity of the subjects of the trial; or
- (b) the scientific value of the trial.”

In the event that a serious breach is suspected the Sponsor must be contacted within 1 working day. In collaboration with the CI the serious breach will be reviewed by the Sponsor and, if appropriate, the Sponsor will report it to the REC committee, Regulatory authority and the relevant NHS host organisation within seven calendar days.

**University of
Nottingham**
Health Service

15. Ethical and regulatory considerations

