18.	Development of a new product/process or the generation of intellectual property	31
19.	References	32
20.	Appendices	34
20.1	Vitamin D Supplementation	34

**University of
Nottingham**
Health Service

3. Plain English Summary

Vaccines help us prevent diseases and keep us well. Some vaccines work better than others and there are many reasons for this. It can be to do with the vaccine itself or to do with the person having the vaccine. We have already found that people who report feeling happier on the day they are vaccinated produce more antibodies in response to the vaccination. We have also found that giving people only 15 minutes of a positive mood intervention to watch before they are vaccinated improves their mood. Recent research also suggests that the amount of vitamin D in your body at the time of vaccination can affect how well vaccines work.

In this study we will conduct a small experiment in which people who are about to receive a COVID-19 or influenza vaccination, or both, will be put in one of 4 groups at random.

- Group 1 will not be offered anything other than their vaccine (this is called usual care).
- Group 2 will receive a brief positive mood intervention, which has previously been shown to improve mood on the day they are vaccinated and for a further 6 days. They will also be advised to take a single dose of a vitamin D tablet just before they are vaccinated and once daily for the following 27 days.
- Group 3 will also receive the positive mood intervention on the day they are vaccinated and for a further 6 days, but they will not take the vitamin D tablet.
- Group 4 will be advised to take a vitamin D tablet at the time of vaccination and once daily for the following 27 days.

We will ask all participants to provide 15ml blood samples before vaccination and then at 28 days and at 6 months post vaccination. This sample will help us measure antibody responses to the vaccination and determine how well people have responded. In addition, up to 20 people across all groups will be asked to provide up to a 60ml blood sample at baseline and at day 28. These samples will allow us to understand how our interventions are changing the way the immune system works.

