Finally, we will also interview a small number of participants as well as people working in vaccine clinics to gain their views on our approach to improving vaccine effectiveness. This work will help to identify if there is an easy and effective way to make vaccines work better that is acceptable to doctors and patients, doesn't have any side effects and which anyone, anywhere can try.

4. Synopsis

Study title	A feasibility randomised controlled trial examining the effect of a positive mood intervention and vitamin D supplementation on the immunological responses to a boosting COVID-19 and/or influenza vaccination in healthy adults		
IRAS reference	316876		
Short title	PROTECTIVE-D: imPROving the effecTivenEss of vaccinaTion wltH positive mood and Vitamin D		
Participants	Adults aged 65 years and over eligible for COVID-19 booster vaccination in Autumn 2022		
Sample size	~40		
Treatment	Positive mood intervention +/- vitamin D supplementation		
Treatment duration	7-28 days		
Study duration	12 months		
Planned study period	November 2022 to November 2023		
Objectives	Outcome measures	Evaluation time points	
Primary	Feasibility and acceptability of study interventions for testing in future studies	Qualitative assessment of acceptability of interventions. Intervention adherence measures.	4 weeks

**University of
Nottingham**
Health Service

Exploratory	Assessment of effectiveness of study intervention in improving immune response to COVID-19 boosting and/or influenza vaccination.	Anti-SARS-CoV-2 immunoglobulin levels +/- vaccine induced influenza immunoglobulin levels	4 weeks 24 weeks
	Further investigate immunological response to intervention.	SARS-CoV-2/influenza neutralising antibodies and T-cell responses.	4 weeks

**University of
Nottingham**
Health Service

5. Abbreviations

AE:	Adverse Event
AR:	Adverse Reaction
CI:	Chief Investigator
CRF:	Case Report Form
CTIMP:	Clinical Trial of Investigational Medicinal Product
DSUR:	Development Safety Update Report
EudraCT:	European Clinical Trial Database
FDA:	Food and Drug Administration
GCP:	Good Clinical Practice
GDPR:	General Data Protection Regulation
HRA:	Health Research Authority
ICF:	Informed Consent Form
ISF:	Investigator Site File
PI:	Principal Investigator
PIS:	Participant Information Sheet
PPI:	Patient and Public Involvement
REC:	Research Ethics Committee
SAE:	Serious Adverse Reaction
SAE:	Serious Adverse Event
SOP:	Standard Operating Procedure
SUSAR:	Suspected Unexpected Serious Adverse Reaction

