8.3 Exclusion criteria

- Participants who have enrolled on a COVID-19 vaccine clinical trial of investigational medicinal product (CTIMP) in the last 12 months.
- Participants who are clinically extremely vulnerable and received a third or fourth dose in Spring 2022.
- Those aged less than 65.
- Those ineligible to receive a COVID-19 and/or influenza vaccination as part of usual care or those for whom a COVID-19 and/or influenza vaccination is contraindicated.
- Those for whom the collection of blood samples is contraindicated.
- Deemed by health care provider to be:
 - Too physically frail to participate.
 - Diagnosed with dementia or other cognitive condition which would make participation difficult.
 - Insufficient command of English language to complete surveys and provide informed consent.
- Participants who, in the past 3 months, have been prescribed oral vitamin D supplementation by a health care professional or who take over the counter supplements regularly on the advice of a health care professional.

9. Study Design

This study aims to evaluate the feasibility of large-scale testing of the intervention in future trials by evaluating its acceptability to participants and adherence markers. Samples will be taken at various timepoints during the study and Adverse Events, Severe Adverse Events and Adverse Events of Special Interest will be recorded. Figure 1 below displays the activities for the study.

[figure not shown]

Figure 1 displays a flow chart of the proposed study design.

**University of
Nottingham**
Health Service

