9.8 Discontinuation/withdrawal of participants

Each participant may exercise their right to withdraw from the study at any time. In addition, the investigator may terminate the participant's involvement in the study at any time if the investigator considers it necessary for any reason including, though not exclusive to, the following:

- Ineligibility (either arising during the study or in the form of new information not declared or detected during the eligibility assessment)
- Significant protocol deviation
- Significant non-compliance with study requirements
- Any adverse event which requires discontinuation of the study procedures or results in an inability to continue to comply with study procedures
- Consent withdrawn
- Lost to follow up

The reason for withdrawal will be recorded in the study records, the withdrawn participants will not be replaced. Withdrawal from the study will not result in exclusion of the data generated by that participant from analysis unless requested by the participant.

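### Section 11.3 limits the analysis to e-diary completers without major violations, so adherence, part of the primary outcome, is estimated in a selected group and is likely overstated

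*Protocol*

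**What the plan says.** The Synopsis gives the primary objective as "Feasibility and acceptability of study interventions for testing in future studies", with outcome measures "Qualitative assessment of acceptability of interventions. Intervention adherence measures", evaluated at 4 weeks. Section 9 (Study Design) says the study judges feasibility by "evaluating its acceptability to participants and adherence markers".

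Section 11.3 then fixes the analysis population. Participants must have no major protocol violation, a term that is not defined, and the set will "comprise all participants, who complete the e-diary (and consent form) and for whom post-baseline assessment of the primary outcome measure is available". Its second paragraph brings in everyone enrolled, but for laboratory data only.

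Five other places bear on this:

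- **9.7** defines compliance as a proportion of participants. The conditions are a completed diary, at least one SARS-CoV-2 vaccine dose, a pre-vaccination blood sample and at least one later sample.
- **7 and 9.3** tie the e-diary to the daily intervention reminders. Section 9.3 allows paper copies or phone calls for those who cannot use it.
- **9.8** lists "Significant non-compliance with study requirements" among the grounds on which the investigator may end participation. It then says: "Withdrawal from the study will not result in exclusion of the data generated by that participant from analysis unless requested by the participant".
- **11.1** says recruitment, study procedures and retention will be assessed to plan a larger trial.
- **11.2** says missing data will not be imputed.

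**The concern.** Whether a participant finishes the diary is known only after randomisation, and the protocol itself treats it as part of compliance. A set defined by diary completion therefore selects on the outcome. People who lose interest in the sessions or tablets are also plausibly the people who stop answering the daily message. If they leave the denominator, the adherence estimate describes only those who stayed engaged.

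In a feasibility trial that estimate is a main product. Section 11.1 has the steering group decide, at about 40 participants, whether the data suffice to design the larger trial, including whether the adherence measures are working as intended. Diary non-completion is direct evidence on that question, and 11.3 leaves it out of view. The exploratory laboratory outcomes get an all-enrolled analysis, while adherence, a primary measure, gets a completer analysis.

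**Working it through.** **Figures in the plan.** The protocol states no adherence rate, diary completion rate, or power or sample size calculation on this point, so there is no figure to reproduce. The recruitment totals in 11.1 agree with their per-arm minimums: 4 × 10 = 40 and 4 × 20 = 80. All rates below are assumptions, used only to show size.

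**Step 1: compliance as defined in 9.7.** Let q be the share of randomised participants who complete the diary, and r the share of those completers who also meet the vaccine and blood-sample conditions.

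- In all randomised participants, compliance = q × r.
- In the 11.3 set, everyone has completed the diary, so compliance = r (ignoring the set's other conditions).

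With q = 0.80 and r = 0.90, this is 0.72 against 0.90. With q = 0.70 and r = 0.90, it is 0.63 against 0.90. The diary component is 100% in the 11.3 set whatever q is.

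**Step 2: adherence, starting from the true rate.** Let p be true adherence, q1 the diary completion rate among adherers and q0 the rate among non-adherers. Adherence among diary completers is

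p·q1 / (p·q1 + (1 − p)·q0).

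With p = 0.60:

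| q1 | q0 | Calculation | Diary completers | Excess over 60% |
|---|---|---|---|---|
| 0.90 | 0.50 | 0.54 / (0.54 + 0.20) = 0.54/0.74 | 73% | 13 points |
| 0.95 | 0.50 | 0.57 / (0.57 + 0.20) = 0.57/0.77 | 74% | 14 points |
| 0.90 | 0.30 | 0.54 / (0.54 + 0.12) = 0.54/0.66 | 82% | 22 points |
| 0.95 | 0.20 | 0.57 / (0.57 + 0.08) = 0.57/0.65 | 88% | 28 points |

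**Step 3: the same question from the completers' side.** Let a1 and a0 be adherence in diary completers and non-completers. Adherence in all randomised participants is q·a1 + (1 − q)·a0, whereas the completer set estimates a1. Take a1 = 0.90:

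| q | a0 = 0.5 | a0 = 0.2 | a0 = 0 |
|---|---|---|---|
| 0.80 | 0.82 | 0.76 | 0.72 |
| 0.70 | 0.78 | 0.69 | 0.63 |

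The completer set shows 0.90 throughout, an overstatement of 8 to 27 points. If a0 = a1 there is no bias.

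**Step 4: at the trial's size.** Take 30 participants in the three intervention arms (3 × 10). Suppose 21 complete the diary and 19 of them adhere, while 9 do not complete it and 2 of them adhere. Diary completers give 19/21 = 90% (95% Wilson interval 71% to 97%). All randomised give (19 + 2)/30 = 21/30 = 70% (52% to 83%).

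**The case against.** The best defence is that 11.3 may not have been meant to govern every feasibility proportion. The 9.7 measure would be partly trivial inside a completer set, and the retention promised in 11.1 cannot be read from a set that requires a post-baseline outcome. On that view the fault is unclear scope. This has force as to intent, but the protocol states no other population for adherence, so an analyst following it would use 11.3. Serum vitamin D (9.6) is laboratory data and so is kept for everyone enrolled. The protocol does not name it as an adherence measure, however, and it says nothing about the mood sessions.

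Several stronger readings are tempting and are not supported:

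- *That all non-adherent participants are removed.* Someone who records missed tablets or sessions in a completed diary stays in. Whether non-adherence is a major violation is undefined.
- *That upward bias is certain.* It requires non-completers to adhere less than completers. That is plausible, but no figure in the protocol shows it.
- *That acceptability is biased too.* It is assessed qualitatively. The interviews in 9.4 use purposive sampling and carry no diary condition.
- *That 9.8 drops non-compliers from the denominator.* It allows participation to end for non-compliance, but keeps the data already generated. It pulls against 11.3 rather than removing anyone.
- *That usual care cannot enter the set.* Section 9.3 describes the diary only for intervention groups, and the Plain English Summary says "Group 1 will not be offered anything other than their vaccine (this is called usual care". That sentence concerns what is offered, not what is recorded, and 9.7 speaks of participants generally. This is an ambiguity to settle.

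It is also fair to object that counting every blank diary day as not taken would sit badly with 11.2 and could understate adherence. That rule therefore belongs in a sensitivity analysis. The change of denominator does not depend on it.

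**Conclusion.** The point holds for adherence and for compliance as defined in 9.7. Section 11.3 conditions a primary measure on diary completion, absence of an undefined major violation, and availability of the outcome itself. That the diary component of compliance becomes 100% follows from the text alone. The overstatement of adherence is likely rather than proven: about 13 to 28 points under the assumptions in step 2 and 8 to 27 under those in step 3. A reader should not carry these figures over as estimates for this trial. Section 11.3 is also in tension with 9.8, which keeps withdrawn participants' data, and with the aim in 11.1 of assessing retention. No adherence threshold is set for the steering group's decision, so the harm is a misleading planning figure rather than a wrongly triggered rule.

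**What to change.** Replace the first paragraph of 11.3 with wording to this effect:

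> Adherence, compliance (9.7), diary completion and retention are analysed in all randomised participants by allocated group. For adherence to each intervention component, the denominator is everyone allocated to that component. Non-compliance, withdrawal or an incomplete diary does not remove a participant from the denominator. Missing diary data are reported separately by group. Bounding sensitivity analyses count days without an entry as not taken and, alternatively, use recorded days only. Participants without major protocol violations who completed the diary form a sensitivity set.

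Then make four small alignments:

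- Say in 11.2 that the bounding analyses are sensitivity analyses and do not replace missing values in the main analysis.
- Respect the 9.8 provision for participants who ask that their data be excluded, and report how many do so.
- Accept the paper or telephone diaries of 9.3 as diary completion, and define a major protocol violation.
- State whether usual-care participants complete a diary.

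The change is to protocol wording only and needs no extra participants or visits. The downside is a possibly lower adherence figure, with the uncertainty from missing diaries shown openly.
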